15.4 Analysis of Secondary Endpoints

Safety and tolerability data will be summarized by each secondary endpoint.

The mean maximum LSR composite score, the VAS score, and the Skindex-16 scores and trend in scores over the study visits will be reported as descriptive data. The composite LSR score will be compared to historical controls (Lebwohl et al, NEJM 2012).

The efficacy analysis will be based on the intent-to-treat (ITT) population. In the ITT population, patients will be counted in the treatment group upon informed consent, and receipt of at least one dose of study medication.

For efficacy analysis, all missing values due to patient early termination from the study will be imputed using last observation carried forward (LOCF) method, as appropriate. For each patient, the Baseline values will be defined as those values recorded at Day 1 prior to dosing or Screening as appropriate. Patients who are lost-to-follow-up after Baseline will be included to the ITT population carrying forward their Baseline values, i.e., these patients will be considered as treatment failures.

Percent reduction in number of actinic keratoses and proportions of patients with partial and complete clearance of actinic keratoses will be presented descriptively and visualized as histograms. These scores will be compared to historical controls (Lebwohl et al, NEJM 2012).

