7.1 Allowed Medications and Treatments

Standard therapy for OTR is allowed except for treatments noted in the exclusion criteria described above and as noted in the prohibited medications section below.

If a patient has a (1) local skin response score of 3 or greater in any individual category, and (2) associated symptoms unrelieved by supportive care such as ice packs and nonsteroidal anti-inflammatory drug (NSAID), then 1% topical hydrocortisone cream or ointment is allowed after Day 4 at the discretion of the investigator.

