9.1.6 Local Skin Response (LSR)

LSR is measured by visual assessment by the investigator using a 4 point scale on 6 responses for a maximum total of 24. The points are assessed using the LSR scale (Appendix III) : The 6 responses are: Erythema, Flaking/Scaling, Pustulation/Vesiculation, Crusting, Swelling, and Erosion/Ulceration. The mean maximum LSR composite score and trend in score over the study visits will be reported as descriptive data and compared to historical controls. LSR assessment will performed at every visit.

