APPENDIX III. LOCAL SKIN RESPONSE ASSESSMENT

Grade	0	1	2	3	4
Erythema	Not present	Slightly pink <50%	Pink or light red >50%	Red, restricted to treatment area	Red extending outside treatment area
Flaking/Scaling	Not present	Isolated scale, specific to lesions	Scale <50%	Scale >50%	Scaling extending outside treatment area
Crusting	Not present	Isolated crusting, specific to lesions	Crusting <50%	Crusting >50%	Crusting extending outside treatment area
Swelling	Not present	Slight, lesion specific edema	Palpable edema extending beyond individual lesions	Confluent and/or visible edema	Marked swelling extending outside treatment area
Vesiculation/Pustulation	Not present	Vesicles only	Transudate or pustules, with or without vesicles, <50%	Transudate or pustules, with or without vesicles, >50%	Transudate or pustules, with or without vesicles, extending outside treatment area
Erosion/Ulceration	Not present	Lesion specific erosion	Erosion extending beyond individual lesions	Erosion >50%	Black eschar or ulceration

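### Both planned summaries of local skin response rest on a sum of six unlike signs, which can mask a severe reaction in one sign

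*Combined protocol and SAP*

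**What the plan says.** Section 15.4 plans to report as descriptive data "The mean maximum LSR composite score, the VAS score, and the Skindex-16 scores", and the same sentence adds the trend in these scores across visits. Section 9.1.6 says: "The mean maximum LSR composite score and trend in score over the study visits will be reported as descriptive data and compared to historical controls". The statistics part of the synopsis repeats the plan of section 15.4. The external comparison uses the total: "The composite LSR score will be compared to historical controls".

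Appendix III grades erythema, flaking/scaling, crusting, swelling, vesiculation/pustulation and erosion/ulceration from 0 to 4. The top grade of erosion/ulceration is "Black eschar or ulceration". Section 9.1.6 gives the maximum total as 24.

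Outside the analysis sections, the protocol does use single-sign grades. Sections 2.1 and 7.1 make a "local skin response score of 3 or greater in any individual category" one of two conditions for permitted hydrocortisone. The other condition is symptoms that supportive care has not relieved.

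The primary endpoint (5.1, 15.3) is the incidence of patients with any adverse event, with a serious adverse event, and with an adverse event leading to drug discontinuation. Severity is recorded for each adverse event (9.1.10, 11.1).

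**The concern.** Section 2.1 names local site reactions as the main risk of the drug. Section 2 describes treating up to 100 cm² against a labelled 25 cm², a factor of 100/25 = 4, in a population for which it says no safety data exist. Section 3.2 makes LSR a secondary objective. A reader will want to know how many patients had a severe reaction, and of which kind. A total over redness, scaling, crusting, swelling, vesicles and ulceration does not show this, and neither does a mean or a time course of that total. The LSR results could therefore look mild while some subjects had a high grade in the sign that matters most.

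**Working it through.** **1. The scale.** Six signs (9.1.6) times a top grade of 4 (Appendix III) gives 6 × 4 = 24, the stated maximum. Grades 0-3 would give 6 × 3 = 18, so the composite uses 0-4.

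**2. Ordering.** Grade 4 erosion/ulceration with nothing else scores 4. Grade 1 in all six signs scores 6 × 1 = 6 and ranks as worse.

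**3. Overlap.** With grade 4 erosion/ulceration the other five signs add 0 to 20, so the composite lies between 4 and 24. With no sign at grade 3 or above, it lies between 0 and 6 × 2 = 12. Any composite from 4 to 12 fits both kinds of subject.

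**4. Effect on the mean.** I read the mean maximum as the mean over subjects of each subject's highest composite. If k of n subjects go from 0 to 4 in one sign at their peak visit, other signs unchanged, the mean rises by 4k/n:
- n = 20 (section 4.1), k = 1: 4/20 = 0.20 points, or 0.20/24 = 0.8% of the scale
- n = 20, k = 2: 8/20 = 0.40 points
- n = 10 (one transplant subgroup), k = 1: 4/10 = 0.40 points

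A rise from grade 1 or 2 to grade 4 in one of 20 subjects gives 3/20 = 0.15 or 2/20 = 0.10.

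**5. Spread need not reveal it.** Take assumed grades in the order of Appendix III. Twenty subjects at (2,2,2,1,1,0) each total 8, so the mean is 8.0 and the SD 0. Replace five of them by (2,1,1,0,0,4), which also totals 8. The mean is still 8.0 and the SD still 0, yet 5/20 = 25% now have grade 4 erosion/ulceration.

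**6. The trend.** If the trend follows the composite, steps 2 to 5 apply at each visit. It adds timing, not sign.

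**7. The adverse event route.** Section 11.1 defines an adverse event broadly and neither includes nor excludes LSR findings by name.
- If LSR findings are recorded as adverse events, the any-event component counts slight pinkness and an eschar alike, and section 15.3 plans no table by grade.
- If they are not, an eschar is counted only if the investigator judges it an adverse event on other grounds.
- Discontinuation helps little. Dosing is on Days 1 to 3 and the next scheduled visit is Day 4 (10.2, 10.3), so a reaction first recorded there follows the last planned dose.

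**8. What a count would show.** Exact (Clopper-Pearson) 95% intervals:
- 0/20: upper limit 1 − 0.025^(1/20) = 16.8%
- 1/20 = 5.0%: lower limit 1 − 0.975^(1/20) = 0.1%; upper limit, the 97.5th percentile of Beta(2, 19), = 24.9%
- Subgroup of 10: 0/10, upper limit 30.8%; 1/10 = 10%, 0.3% to 44.5%

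**The case against.** The strongest reply is that the composite is a secondary summary and that severe reactions have another way into the results. The primary endpoint counts patients and is not averaged. It includes events found by physician evaluation, the adverse event definition would admit an eschar, severity is recorded, and the treatment area is photographed from Day 1 onward (9.1.9). Section 15.4 also says: "Safety and tolerability data will be summarized by each secondary endpoint". Section 15 promises a detailed SAP, where tables by sign and grade would be ordinary content.

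Much of this stands, and it limits the point. A reader might infer that the composite is the only LSR summary, but a trend over visits is planned too. A reader might infer that severe reactions drop out of the study or that local tolerability goes unanswered. The documents do not support that: adverse events, pain and Skindex-16 all bear on tolerability. A reader might also take grade 3 in one category as the protocol's own threshold of clinical relevance, but sections 2.1 and 7.1 make it one of two joint conditions, and grade alone triggers nothing. The cohorts in step 5 are constructed, so they show what is possible and not what is likely. A descriptive report also need not omit ranges or individual values.

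The reply still leaves the gap open. The adverse event route is not assured (step 7). The general sentence in 15.4 names no summary by sign, and section 15 does not say that the SAP will add one.

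**Conclusion.** The point holds in a limited form. As planned, the LSR results can mask a severe reaction confined to one sign: a single grade 4 erosion/ulceration shifts a 20-subject mean by at most 0.2 of 24 points, and composites from 4 to 12 cannot separate it from a reaction with no sign at grade 3 or above. The adverse event data may show it, but nothing in the plan ensures that. This rests on the reading of the mean maximum in step 4 and on 20 assessed subjects; section 12.4 does not replace withdrawals, so n may be smaller. It is a worthwhile, inexpensive improvement to how the LSR objective is reported. It is no reason to drop the composite or to change the sample size.

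**What to change.** In sections 15.4 and 9.1.6 and the synopsis, or in the SAP promised in section 15:

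- Keep the composite, its trend and its historical comparison.
- For each of the six signs, report the number and percent of subjects by worst post-dose grade. Post-dose means Day 4 onward, because section 10.2 lists the Day 1 assessment before the first application.
- For each sign, give the counts at grade 3 or above and at grade 4, with exact 95% intervals. The denominator is the subjects with a post-dose LSR assessment.
- Make any pooled count of subjects with some sign at grade 3 or above secondary, and show it with and without erythema. Erythema reaches grade 3 when it is red within the treatment area, so a pooled count would mix redness with erosion.

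A sentence in section 11.1 on whether and when an LSR finding is also recorded as an adverse event would help interpretation, but the table does not depend on it.

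The cost is one extra table and some wording. Appendix III already requires the six grades; I assume that the case report form keeps them separately, as it is not among the documents. No visit or assessment is added. The intervals will be wide at n = 20, and wider in each subgroup of 10, and the text should say so.

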	
safety evaluation.
 
Adverse events will be explored for trends or heterogeneity between the two transplant subgroups; lung and kidney. If there is evidence for a difference between groups, the subgroups will be reported separately.
 
The mean maximum LSR composite score, the VAS score, and the Skindex-16 scores and trend in scores over the study visits will be reported as descriptive data. The composite LSR score will be compared to historical controls (Lebwohl et al, NEJM 2012).
 
The efficacy analysis will be based on the intent-to-treat (ITT) population. In the ITT population, patients will be counted in the treatment group upon informed consent, regardless of receiving any dose of study medication.
 
For efficacy analysis, all missing values due to patient early termination from the study will be imputed using last observation carried forward (LOCF) method, as appropriate. For each patient, the Baseline values will be defined as those values recorded at Day 1 prior to dosing or Screening as appropriate. Patients who are lost-to-follow-up after Baseline will be included to the ITT population carrying forward their Baseline values, i.e., these patients will be considered as treatment failures.
 
Percent reduction in number of actinic keratoses and proportions of patients with partial and complete clearance of actinic keratoses will be presented descriptively and visualized as histograms. These scores will be compared to historical controls (Lebwohl et al, NEJM 2012).

Rationale for Number of Subjects
	
This is a pilot descriptive sample, not powered for analysis. The sample size of 20 patients is selected to achieve a reportable sample size in two subgroups of organ transplant recipients.

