4 STUDY DESIGN

4.1 Study Overview

This is a single arm, open-label interventional study of ingenol mebutate 0.015% in solid organ transplant recipients. Twenty subjects are planned; 10 kidney transplant recipients and 10 lung transplant recipients. These populations have been selected as they represent the spectrum of solid organ transplantation: kidney transplant recipients are the largest transplant population, but have lower levels of immunosuppression and skin cancer risk. Lung transplant recipients have the highest burden of skin cancer and actinic keratoses.

Screening data will be reviewed to determine subject eligibility. Subjects who meet all inclusion criteria and none of the exclusion criteria will be enrolled into the study.

The following treatment regimens will be used:

- Experimental treatment: Ingenol mebutate 0.015%, topical gel
- Placebo or Comparator: None

Total duration of subject participation will be 57 days. Total duration of the study is expected to be 8 months.

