10.1 Visit 1 (Screening, Day -14 to 1)

1. Review the study with the subject and obtain written informed consent and HIPAA authorization.
2. Assign the subject a unique screening number.
3. Record demographics data.
4. Record medical history, including a history of actinic keratosis, diagnosis date, and prior actinic keratosis treatments.
5. Record concomitant medications.
6. Perform a complete physical examination.

7. Perform an actinic keratosis count.
8. Collect blood for clinical laboratory tests (chemistry and hematology).
9. Collect urine sample and perform urine pregnancy test (if applicable).
10. Continue to Visit 2 procedures (can occur on the same day), or schedule subject for Visit 2/ Day 1.

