15.1 Data Sets Analyzed

All eligible patients who are enrolled in the study and receive at least one dose of the study drug (the Safety Population) and who have had at least one post-baseline safety evaluation will be included in the safety analysis.

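### The efficacy ITT set is everyone who consents in the synopsis but only dosed patients in section 15.4, so the denominator of the clearance rates is not fixed

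*Combined protocol and SAP*

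**What the plan says.** Both the Statistics part of the protocol synopsis and section 15.4 base the efficacy analysis on an ITT population. They then define it differently:

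- Synopsis: "patients will be counted in the treatment group upon informed consent, regardless of receiving any dose of study medication".
- Section 15.4: "patients will be counted in the treatment group upon informed consent, and receipt of at least one dose of study medication".

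Section 15.1 does not decide between them. It describes "All eligible patients who are enrolled in the study and receive at least one dose of the study drug (the Safety Population" and so on, which is the set for the safety analysis; it gives no efficacy set.

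On the order of events, the first item of the Screening visit in section 10.1 is "Review the study with the subject and obtain written informed consent and HIPAA authorization". The actinic keratosis (AK) count is item 7 of that visit. Section 4.1 adds: "Screening data will be reviewed to determine subject eligibility". Consent therefore comes before eligibility is known and before any dose.

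On missing efficacy data, the synopsis and section 15.4 agree with each other. First, "missing values due to patient early termination from the study will be imputed using last observation carried forward (LOCF) method, as appropriate". Second, "Patients who are lost-to-follow-up after Baseline will be included to the ITT population carrying forward their Baseline values", with the gloss that "these patients will be considered as treatment failures".

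**The concern.** The two ITT definitions differ by every patient who consents and is never dosed. On the synopsis wording such a patient is in the denominator; on the 15.4 wording the patient is not. Percent reduction, partial clearance and complete clearance are all computed on this set and then set against published historical controls, so the same data can yield two different rates depending on which page the analyst follows.

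The timing adds to this. Section 15 promises a detailed SAP before the final data are analysed. However, the study is open-label and section 14 says the investigator has access to all study data, so a choice left until then could be made with outcomes known.

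The missing-data rules raise a lesser question. The plan does not say whether loss to follow-up counts as a form of early termination, or which rule applies when a lost subject has a count after Baseline. Section 12.1 lists loss to follow-up among the reasons for early discontinuation, so the two categories can overlap.

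**Working it through.** **Planned size.** Section 4.1 plans 10 kidney and 10 lung recipients: 10 + 10 = 20, as stated. Section 15.6 says the sample is not powered, so there is no power calculation to reproduce.

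**Step 1: who is in each set.**

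| Patient | Synopsis ITT | Section 15.4 ITT |
|---|---|---|
| Consented, dosed | in | in |
| Consented, eligible, never dosed | in | out |
| Consented, fails screening | in, read literally | out |

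The synopsis set is also hard to analyse. A patient who leaves after consent but before the AK count has no Baseline count, and percent change is undefined for a patient whose count is zero. Neither missing-data rule clearly covers an undosed screen failure, so scoring one as a failure is an assumption of this check.

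**Step 2: effect on a clearance rate.** Inputs: 20 dosed (the planned number), r responders, u undosed patients scored as failures. The documents give neither r nor u, so both are assumed.

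Section 15.4 rate = r/20. Synopsis rate = r/(20 + u). With r = 10:

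| u | Synopsis rate | Exact 95% interval |
|---|---|---|
| 0 | 10/20 = 50.0% | 27.2 to 72.8 |
| 1 | 10/21 = 47.6% | 25.7 to 70.2 |
| 3 | 10/23 = 43.5% | 23.2 to 65.5 |
| 5 | 10/25 = 40.0% | 21.1 to 61.3 |

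For a dosed-set rate p, the drop is p × u/(20 + u). With u = 1 it is 0.30 × 1/21 = 1.4 points at p = 30% and 0.70 × 1/21 = 3.3 points at p = 70%. With u = 5 it is 6.0 and 14.0 points.

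If the 20 planned subjects already include the undosed, two undosed give 9/18 = 50% (dosed) against 9/20 = 45% (consented), and four give 8/16 = 50% against 8/20 = 40%.

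**Step 3: where the missing-data rules overlap.** Section 9.1.5 schedules AK counts at Screening, Day 1, Day 29, Day 57 and early termination.

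- Lost with no count after Baseline: the last observation is Baseline, so both rules give the same answer.
- Lost after Day 29 with no later count: LOCF carries the Day 29 count; the lost-to-follow-up rule carries Baseline.
- Stopped treatment early, had the early-discontinuation visit and was later lost: section 12.1 asks for that visit and then encourages the remaining visits, and section 10.7 includes an AK count. LOCF carries the latest post-baseline count; the lost-to-follow-up rule carries Baseline.

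A lost subject who was clear at the last count is a responder under LOCF and a failure under the other rule. One such subject moves a clearance rate by 1/20 = 5 points, for example 10/20 = 50% to 9/20 = 45%. Mean percent change also moves by 100/20 = 5 points, because that subject contributes 0% instead of -100%.

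**The case against.** The strongest reply on the ITT set is that it was never meant to include screen failures. The synopsis speaks of patients counted in the treatment group, and section 4.1 enrols only those who meet the criteria. On that reading the two sets differ only by enrolled patients who are never dosed. These may be few: section 10 lets Screening and Visit 2 fall on the same day, and section 10.2 has the first application done in clinic at Visit 2. This stands as a limit on size. A reader might infer that several screen failures will dilute the rates by 10 points or more, but the documents give no counts and nothing in them makes that likely. The contradiction remains, because the synopsis expressly disregards dosing and 15.4 requires it.

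It can also be said that section 15 governs, since it calls itself the analysis plan that the SAP may modify. That supports correcting the synopsis rather than 15.4, but no text says that the body overrides the synopsis.

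On missing data, the lost-to-follow-up sentence is specific and unqualified, and most naturally means failure whatever was counted earlier. A reader might infer that the two rules flatly contradict each other. They do not: the wording is the same in both places and a sensible reading exists. What is missing is a statement of precedence. A reader might also infer that the rules diverge only for losses between Day 29 and Day 57 without an exit count. Sections 12.1 and 10.7 do not support that limit, because a count at an early-discontinuation visit can be followed by later loss.

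Finally, the interval around 10/20 is far wider than a shift of a few points. That is true, but imprecision is no reason to leave the denominator open.

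**Conclusion.** The contradiction in the efficacy ITT definition is plain on the text and should be corrected. Its size depends on how many patients consent and are never dosed, which the documents do not give. With 10 responders among 20 dosed and undosed patients scored as failures, the rate falls from 50.0% to 47.6% with one and to 43.5% with three; with none it does not change.

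The missing-data overlap is an ambiguity of lesser weight. It matters only if a subject is lost after a post-baseline AK count, and then by 5 points in 20 for each one who was clear at that count.

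It would be wrong to infer that the main result of the trial is at risk. The primary endpoint is safety and has its own population, no alpha or power is involved, and only secondary, descriptive endpoints are touched. The consequence is confined to how those endpoints read beside the historical controls.

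**What to change.** 1. Change the synopsis so that its ITT definition matches section 15.4: informed consent and at least one dose.
2. Report the numbers consented, dosed and with a Day 57 AK count, so that a reader can see the effect of the denominator.
3. In both the synopsis and section 15.4, state that for a subject lost to follow-up who has a post-baseline AK count, from Day 29 or an early-discontinuation visit, the lost-to-follow-up rule takes precedence: Baseline carried forward, treatment failure.
4. State that LOCF stays in force for other early terminations, including withdrawal of consent after Day 29. Turning those subjects into failures as well would change the plan rather than clarify it.

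The cost is a few sentences in the synopsis and section 15.4, carried into the promised SAP before the final data are analysed. No visit or data item is added. The downside is that clearance rates may be slightly less favourable than under LOCF if subjects who were clear are later lost.

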2 STUDY RATIONALE

Actinic keratoses (AK) are precursors to cutaneous squamous cell carcinoma (SCC), and are treated to prevent progression to SCC. First-line therapy for AK include cryotherapy and curettage, which target clinically visible lesions but do not address the subclinical lesions in the field of ultraviolet radiation damage. Field therapy includes topical chemotherapy, immunotherapy, and photodynamic therapy. Ingenol mebutate is the active compound found in *Euphorbia peplus* sap, and has been approved for treatment of actinic keratoses in immunocompetent patients. Ingenol mebutate 0.015% is favored over other topical treatments for treatment of actinic keratoses on the face due to the brief treatment course, high clearance rate, and resolution without sequelae.

There are no data on safety of this medication in immunosuppressed solid organ transplant recipients (OTR). OTR have a high incidence of AK and high risk of developing SCC, and require frequent field therapy. In addition, OTR generally have a higher burden of AK and require treatment of a larger surface area than the 25 cm² area labeled for ingenol mebutate 0.015%. We plan to investigate the safety and efficacy of ingenol mebutate 0.015% in OTR, with a treatment area up to 100 cm².

The rationale for an increased dose and surface area for treatment in this study is that OTR typically have an extensive burden of AK, requiring treatment of larger areas such as those described here. The proposed treatment regimen better reflects the 'real world' need for treatment of a larger surface area while evaluating the safety and local site reactions associated with this treatment regimen.

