6.2 Inclusion Criteria

1. Adults at least 18 years old.
2. Subject must be a solid organ transplant recipient at least one year from the date of transplantation.
3. Subjects must be in stable health as confirmed by medical history, per investigator judgement.
4. Subjects must be able to read, sign, and understand the informed consent.
5. Subjects have at least 4 and no more than 20 clinically typical (non-hyperkeratotic/hypertrophic), visible actinic keratoses in a treatment area of approximately 100cm² on the face. Treatment areas will include a single cheek (nasofacial sulcus to tragus, malar cheekbone to jawline and avoiding the lower eyelid and mouth); the forehead (hairline to eyebrows, extending laterally to the root of the helix).
6. Subject must be willing to forego any other treatments on the face, including cryotherapy, tanning bed use and excessive sun exposure while in the study.
7. Subject is willing and able to participate in the study and to comply with all study requirements including concomitant medication and other treatment restrictions.
8. If subject is a female of childbearing potential she must have a negative urine pregnancy test result prior to study treatment initiation and must agree to use an approved method of birth control while enrolled in the study.

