15.6 Sample Size and Randomization

This is a pilot descriptive sample, not powered for analysis. The sample size of 20 patients is selected to achieve a reportable sample size in two subgroups of organ transplant recipients.

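### The complete-clearance proportion is compared with a historical trial without accounting for baseline lesion count, so it can differ at equal drug effect

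*Combined protocol and SAP*

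**What the plan says.** Section 15.4 presents percent reduction in AK count and the proportions with partial and complete clearance descriptively, then adds: "These scores will be compared to historical controls". The synopsis repeats this. Section 9.1.6 treats the composite local skin response (LSR) in the same way: it "will be reported as descriptive data and compared to historical controls". One published trial is cited as the historical source. No matching, stratification, standardisation or other method is given for either comparison.

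Section 5.2 defines complete clearance as a per-patient, all-or-nothing outcome in the target area. Eligibility in section 6.2 reads: "Subjects have at least 4 and no more than 20 clinically typical (non-hyperkeratotic/hypertrophic), visible actinic keratoses in a treatment area of approximately 100cm²". Section 2 says that "OTR generally have a higher burden of AK and require treatment of a larger surface area than the 25 cm² area labeled".

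AK count is taken at Screening and Day 1 (section 9.1.5). The variables to be summarised under section 15.2 are race, gender, age, height and weight, so baseline AK count is not among them. The study has one arm: "Twenty subjects are planned; 10 kidney transplant recipients and 10 lung transplant recipients". On sample size, section 15.6 says: "This is a pilot descriptive sample, not powered for analysis".

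**The concern.** A patient with 20 lesions has more chances to keep one than a patient with 4, even if the gel works equally well on each lesion. The complete-clearance proportion therefore reflects the lesion counts of the patients enrolled as well as the effect of treatment. When it is set beside a published figure from patients whose counts may differ, the two influences cannot be separated.

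The study has no concurrent comparator, so the historical figure is the only outside benchmark for efficacy. A lower complete-clearance rate could be taken as weaker efficacy under immunosuppression when lesion count alone could produce it. Because section 15.2 does not list baseline AK count, the planned tables would not let a reader judge whether the counts were comparable.

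**Working it through.** **Inputs from the documents.** Eligible count 4 to 20 (section 6.2). Complete clearance means all lesions gone; partial clearance means a reduction of at least 75% (section 5.2). Field about 100 cm² against a labelled 25 cm² (sections 6.2 and 2), so 100/25 = 4 times the labelled area. Planned n = 10 + 10 = 20 (section 4.1). The plan states no historical rate, expected clearance or power, so it has no figure of its own to reproduce.

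**Assumptions, because the documents give no values.** Per-lesion clearance probability q, the same in both studies, from 0.7 to 0.9. Within-patient correlation ρ from 0 to 0.5. Historical counts spread evenly over 4–8; this trial's counts spread evenly over 4–20.

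**Step 1: complete clearance by count, independent lesions.** P(all m lesions clear) = q^m. At q = 0.8: 0.8^4 = 41.0%, 0.8^8 = 16.8%, 0.8^12 = 6.9%, 0.8^20 = 1.2%.

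**Step 2: allow lesions within a patient to be correlated.** Under a beta-binomial model, a = q(1−ρ)/ρ, b = (1−q)(1−ρ)/ρ, and P(all clear) is the product over i = 0 to m−1 of (a+i)/(a+b+i). For q = 0.8, ρ = 0.5 and m = 4: a = 0.8, b = 0.2, and (0.8/1)(1.8/2)(2.8/3)(3.8/4) = 63.8%. At m = 20 it is 47.0%. The fall with count remains but is smaller.

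**Step 3: average over the two assumed count ranges.** Each cell shows mean complete clearance for 4–8 lesions, then for 4–20, then the gap in percentage points.

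| q | ρ = 0 | ρ = 0.1 | ρ = 0.3 | ρ = 0.5 |
|---|---|---|---|---|
| 0.70 | 13.3, 4.7: 8.6 | 20.3, 10.0: 10.3 | 33.1, 23.6: 9.5 | 44.7, 37.6: 7.1 |
| 0.80 | 27.5, 11.8: 15.8 | 36.0, 21.6: 14.4 | 49.2, 39.0: 10.2 | 59.6, 53.1: 6.5 |
| 0.85 | 38.7, 19.2: 19.5 | 47.1, 31.7: 15.5 | 59.3, 49.8: 9.5 | 68.3, 62.6: 5.7 |
| 0.90 | 53.7, 32.2: 21.6 | 61.1, 46.5: 14.6 | 71.0, 63.1: 7.9 | 77.9, 73.5: 4.4 |

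Gaps are taken before rounding. They run from 4.4 to 21.6 points, always against the study with more lesions. If the two count distributions were the same, the gap would be 0 for every q and ρ.

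**Step 4: the other measures.** Expected percent reduction equals q at every m, so it does not shift with count. Partial clearance moves mainly through rounding of the 75% cut-off. At q = 0.8 with independent lesions it is 81.9% (m = 4), 65.5% (m = 6), 79.7% (m = 8) and 80.4% (m = 20), with no steady trend.

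**Step 5: LSR.** The synopsis gives one 0.25 g tube per 25 cm² quadrant and a constant 1.5 mcg per cm². Several Appendix III grades are relative to the field (below or above 50%) or refer to spread beyond it. If each response is graded as a field average, a fourfold area shifts the expected score by 0. If it is graded on the worst of four quadrants, the expected shift is 1.03, 0.73, 0.46 or 0.33 SD at between-quadrant correlation 0, 0.5, 0.8 or 0.9 (simulation, normal scores). The documents do not say which way of grading applies.

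**Step 6: random error.** The exact 95% interval for 8/20 is 19% to 64%.

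**The case against.** The strongest objection is that the bias depends on a source the documents do not reproduce. The historical trial's lesion counts, field size and visit days are not given, and the 4–8 range is an assumption. This stands: the actual gap cannot be computed and may be nil. In section 2 the 25 cm² qualifies surface area, and the higher burden is a separate, qualitative statement. It gives a reason to check the counts but does not establish that they differ from the historical trial's.

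Lesions in one patient share skin, immunosuppression and application technique, so independence gives too large an effect at the higher clearance rates. This also stands, and is why the range extends down to 4 points.

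The comparison is secondary and descriptive, with no test or decision rule, and section 15 promises a detailed SAP. That limits the consequence to interpretation. It does not supply a method, and that SAP is a natural place to put one.

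Three stronger readings are tempting and are not supported:

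- A reader might infer that every clearance measure is distorted. Step 4 shows that expected percent reduction is not, and that partial clearance varies mainly through rounding.
- A reader might infer that the fourfold field by itself raises LSR. Step 5 shows that this depends on how the field is graded. The factor of four is also relative to the label; the historical trial's field is not stated.
- A reader might infer that the plan intends to attribute differences to transplant status. No section says so.

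**Conclusion.** The point holds for complete clearance. Section 15.4 and the synopsis compare a count-dependent proportion with a historical figure and provide nothing to show or allow for baseline count. Under the two assumed count ranges, the distortion is about 4 to 22 percentage points for q of 0.7–0.9 and ρ of 0–0.5. The direction is the same throughout that grid, but it depends on this trial having the higher counts. A 20-point gap should not be taken as the expected size: it needs high per-lesion clearance and nearly independent lesions as well as the assumed ranges. The true size is unknown. An effect of field size on LSR is possible but not shown. With 20 patients, sampling error is at least as important as this bias. The matter is worth correcting because the remedy is cheap and changes what the comparison can support.

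**What to change.** - **Section 15.2:** add baseline AK count and treated area to the baseline summaries.
- **Section 15.4 and synopsis, lead measure:** make per-patient percent reduction the lead efficacy measure for the historical comparison.
- **Section 15.4 and synopsis, complete clearance:** keep it, but report it with an exact 95% confidence interval and by baseline count (for example 4–8 and 9–20), beside the historical trial's count range.
- **Sections 15.4 and 9.1.6:** state that differences in clearance or LSR cannot be attributed to transplant status, because lesion count, field size and immune status may all differ.

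The cost is a few sentences and one stratified table; AK counts are already collected. The strata will be small: with about 10 patients in each, the exact 95% interval for 5/10 is 19% to 81%, so they show the pattern and do not support a precise estimate. The headline complete-clearance comparison becomes a qualified one.
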